## 5.5.2.7 Morning Dystonia

Patients will be asked if they experienced any morning dystonia within the last week before Visit 2b, Visit 4, Visit 5 and Visit 6/EDV.

The following statistical output will be provided:

Table 15.2.8.1.1 Summary of Morning Dystonia – Full Analysis Set

Table 15.2.8.1.2 Summary of Morning Dystonia – Per-Protocol Set

Morning dystonia evaluation will be summarised for each visit at which the assessment was performed.

Table 15.2.8.2.1 Shift Table of Morning Dystonia – Full Analysis Set

Table 15.2.8.2.2 Shift Table of Morning Dystonia – Per-Protocol Set

Shift tables will be provided showing changes between Visit 2b (baseline) and all post-baseline visits in the number and frequency of patients with morning dystonia (yes) and without morning dystonia (no). Patients with missing data will be presented as part of a "missing" category.

Listing 16.2.3.7 Morning Dystonia – Enrolled Set

Morning dystonia data will be displayed for each patient at all applicable visits in the enrolled set.

#### 5.5.2.8 Use of Rescue Medication

The intake of rescue medication will be recorded in a patient diary. Starting with Visit 2b, the patients will receive a rescue medication diary and will be trained to daily record if any rescue medication was taken or not. In case of intake, the name of the rescue medication (paracetamol or tramadol) and the number of tablets/capsules taken have to be recorded.

The frequency of rescue medication intakes will be summarised by type of rescue medication, by overall and periods as described below:

- overall from first IP intake day to the day before Visit 6/EDV
- from first IP to Visit 4 from first IP intake day to the day before Visit 4
- from Visit 4 to Visit 5 from Visit 4 day to the day before Visit 5
- from Visit 5 to Visit 6 from Visit 5 day to the day before Visit 6
- within 30 days before Visit 4 (this period could contain less than 30 days)
- within 30 days before Visit 5
- within 30 days before Visit 6.

If both medications are used on the same day, then both will be used for calculation. If duplicated entries are present the worst case will be applied for the analysis, i.e. in case a record with and without rescue medication intake is documented in the diary, the record with rescue medication intake will be used.

Additionally, diary adherence by overall and periods will be calculated as:

Diary adherence in period (%) =  $\frac{100 * filled days in period}{end date of period - start date of period + 1}$ 

I-DM-011SAP Page 31 of 49

The frequency of rescue medication intakes and diary adherence will be summarised using data from first IP intake day to the day before Visit 6/EDV. Other collected data outside this period will be listed.

The following statistical output will be provided:

Table 15.2.9.1.1 Summary of Usage Frequency of Rescue Medication - Full Analysis Set

Table 15.2.9.1.2 Summary of Usage Frequency of Rescue Medication – Per-Protocol Set

Usage frequency of rescue medication will be summarised by type of rescue medication, by overall and periods.

Table 15.2.9.2.1 Summary of Rescue Medication Diary Adherence – Full Analysis Set

Table 15.2.9.2.2 Summary of Rescue Medication Diary Adherence – Per-Protocol Set

Rescue medication adherence will be summarised by overall and periods.

#### Listing 16.2.3.8 Use of Rescue Medication – Safety Set

Use of rescue medication data will be displayed for each patient in the safety set.

## 5.6 Safety Analysis

The SS will be used for the analysis of safety data.

#### **5.6.1** Adverse Events

AEs will be coded according to latest MedDRA® Version 23.1.

Adverse event data includes:

- adverse event name
- onset date/time and stop date
- action taken with study medication (dose not changed, dose increased, dose reduced, drug interrupted, drug withdrawn, not applicable, unknown)
- other actions (none, medication required, tests required, hospitalisation required or prolonged, withdrawn from study, other specified)
- outcome of event (recovered/resolved, recovering/resolving, not recovered/not resolved, recovered/resolved with sequelae, fatal, unknown)
- seriousness (yes or no)
- severity (mild, moderate, severe)
- relationship (unrelated, unlikely possible, probable, definite)

All AEs will be presented in listings.

Summaries of AE will include AEs defined as **treatment-emergent adverse events (TEAEs)**, defined as AEs with the first onset or worsening after the first IP intake until 14 days after the last IP intake.

If the start date of an AE is incomplete or missing, it will be assumed to be treatment-emergent except if the incomplete start date or the stop date indicates that the event started prior to the first IP intake or later than 14 days after last IP intake.

Adverse events will be further assigned to the following categories:

- **Serious Adverse Events (SAEs):** defined as AEs considered by the investigator as serious, including AEs with an unknown or missing seriousness assessment.
- **Related TEAEs**: AEs assessed as "Possible", "Definite" or "Probable" to IP, including events with missing IP relationship assessment.
- Unrelated TEAEs: AEs assessed as "Unrelated" or "Unlikely" to IP.
- **Severe TEAEs**: AEs assessed as "Severe" in intensity, including events with missing severity assessments.
- **TEAEs leading to discontinuation:** AEs for which "Action taken with IP" is indicated as "drug withdrawn" or "other actions taken" is "withdrawn from study".
- **TEAEs leading to death:** AEs documented as having a "fatal" outcome.

I-DM-011SAP Page 32 of 49

The following statistical output will be provided:

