At V2b (Day 1) and if eligibility is confirmed, the patient will be randomised to 50 mg opicapone or placebo once daily (1:1) and start treatment in addition to current treatment with L-dopa/DDCI.

Opicapone enhances the effects of L-dopa. Hence, it may be necessary to reduce the patient's L-dopa/DDCI dose within the first days or weeks of opicapone treatment. Therefore, the investigator will call the patient on Day  $8\pm 2$  (V3) to ask for any changes in the medical condition. If dose decrease of L-dopa/DDCI is deemed necessary, it may be adjusted by phone at V3 or an unscheduled on-site visit may be performed at the investigator's discretion. In case of L-dopa/DDCI adjustment an unscheduled phone call should be repeated up to 7 days after dose adjustment or V4 (Day  $29\pm 2$ ) should be performed, whatever applies first. The investigator can decrease the daily dose of L-dopa/DDCI (but keeping the number of daily intakes unchanged) as required until V4. If the investigator finds that the dose reduction was

too much, it can be increased again up to the baseline dose level. The dosage of L-dopa/DDCI should not be changed from V4 through the end of the study. No new anti-PD drugs should be started during the study and any that are ongoing at the start of the study must be kept at a stable dose throughout the study. No new pain medication should be started during the study except the allowed rescue medication. Baseline dose of pain medication may be reduced throughout the study if required due to pain medication-related AEs. If the investigator finds that the dose reduction was too much, it can be increased again up to the baseline dose level.

Further visits will be performed on Day  $85 \pm 4$  (V5, after 12 weeks) and Day  $169 \pm 4$  (V6, after 24 weeks). The primary analysis will be performed on the data collected at V6. A follow-up Visit (FU) will be performed on Day  $183 \pm 4$ , approximately 2 weeks after last intake of the investigational product (IP; 50 mg opicapone or placebo).

Patients who discontinue study participation prematurely will be asked to come to the site for an early discontinuation visit (EDV).

At V6 (or EDV, if applicable) the investigator will arrange for the patient's subsequent treatment, i.e. either prescribe further opicapone or switch to another treatment.

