#### **Exclusion criteria:**

- 1. Non-idiopathic PD (atypical parkinsonism, secondary [acquired or symptomatic] parkinsonism, Parkinson-plus syndrome).
- 2. Severe and/or unpredictable OFF periods, according to investigator judgement.
- 3. Major/prominent non-PD-related pain (e.g. due to malignant disease).
- 4. Treatment with prohibited medication: entacapone, tolcapone, monoamine oxidase (MAO) inhibitors (except selegiline up to 10 mg/day in oral formulation or 1.25 mg/day in buccal absorption formulation, rasagiline up to 1 mg/day or safinamide up to 100 mg/day), or antiemetics with antidopaminergic action (except domperidone) within the last 4 weeks before V1.
- 5. Previous or planned (during the entire study duration) L-dopa/carbidopa intestinal gel infusion, deep brain stimulation or stereotactic surgery (e.g. pallidotomy, thalamotomy).
- 6. Treatment with apomorphine within the last 4 weeks before V1 or likely to be needed at any time until V6.
- 7. Previous or current use of opicapone.
- 8. Use of any other IP, currently or within the 3 months (or within 5 half-lives of the IP, whichever is longer) before V1.
- 9. Past (within the past year) or present history of suicidal ideation or suicide attempts.
- 10. Current or previous (within the past year) alcohol or substance abuse excluding caffeine or nicotine.
- 11. Phaeochromocytoma, paraganglioma, or other catecholamine secreting neoplasms.
- 12. Known hypersensitivity to the excipients of IP (including lactose intolerance, galactose intolerance, Lapp lactase deficiency or glucose-galactose malabsorption) or of rescue medication.
- 13. History of neuroleptic malignant syndrome or non-traumatic rhabdomyolysis.

- 14. History of severe hepatic impairment (Child-Pugh Class C).
- 15. Previous history of psychosis or psychiatric disorders, including severe major depression.
- 16. Any medical condition that might place the patient at increased risk or interfere with assessments.
- 17. For females: Pregnant or breastfeeding.
- 18. Employees of the investigator, study centre, sponsor, clinical research organisation and study consultants, when employees are directly involved in this study or other studies under the direction of this investigator or study centre, and their family members.
- 19. Persons committed to an institution by virtue of an order issued either by the judicial or other authorities.

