- 1) If self-rating diary (Hauser's PD diary) entries are non-compliant, the patient will be re-trained on correct use of the diary and V2b will be postponed for 3 to 4 days. If the patient completed the diary satisfactorily, V2b is to be performed immediately, at the same day.
- 2) If L-DOPA/DDCI adjustment is deemed necessary, an unscheduled on-site visit for dose adjustment may be performed at the investigator's discretion. After L-DOPA/DDCI adjustment, either the phone call should be repeated up to 7 days after dose adjustment or V4 should be performed, whatever applies first.
- 3) An EDV should be performed as soon as possible (not exceeding 7 days) after early discontinuation.
- 4) Only to be performed if V2a and V2b will not take place on the same day.
- 5) The first intake of opicapone will take place on the day of V2b, at least 1 hour before or after the last daily dose of L-DOPA/DDCI.
- 6) In females of childbearing potential.

I-DM-011SAP Page 9 of 49

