**Table 1: IP Description** 

Name of IP	Opicapone	Placebo
Dosage form	Hard capsule	Hard capsule
Active ingredient	Opicapone (BIA 9-1067), (2,5-dichloro-3-[5-{3,4-dihydroxy-5-nitrophenyl}-1,2,4-oxadiazol-3-yl]-4,6-dimethylpyridine 1-oxide)	Not applicable
Strength/concentration	50 mg	Not applicable

The last IP intake will take place in the evening prior to Visit 6. The IP should be taken once daily at bedtime, at least 1 hour before or after the last daily dose of L-DOPA/DDCI. The patients will be instructed to swallow the capsule whole with a glass of water.

I-DM-011SAP Page 11 of 49

In case one dose of IP is missed, the next dose should be taken as scheduled. The patient should not take a double dose to make up for the missed dose.

Patients are allowed to use rescue medication provided by sponsor:

- paracetamol (500 mg tablets; 4 g (3 g for German sites) per day at maximum) (unless patient already receives tramadol)
- tramadol (50 mg capsules; 400 mg per day at maximum).

Concomitant use of both types of rescue medication during the same day is not allowed. In case the patient needs to switch to tramadol, an unscheduled visit for dispensation of tramadol may be performed as required.

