#### 3. ANALYSIS SETS AND SUBGROUPS

#### 3.1 Analysis Sets

The **Enrolled Set** will be defined as all patients who signed informed consent.

The **Randomised Set** will be defined as all randomised patients.

The **Safety Set (SS)** will be defined as all patients randomised who took at least one dose of IP. Subjects will be analysed according to actual treatment taken.

The Full Analysis Set (FAS) will be defined as all patients who were randomised and who had at least one post-baseline assessment of primary efficacy measurement. Subjects will be analysed according to randomised treatment.

The **Per-Protocol Set (PPS)** will be defined as all patients who were included into the FAS and had no major protocol deviations that could have an influence on the primary efficacy endpoint. Subjects will be analysed according to randomised treatment. Patients that will belong to or will be excluded from the PPS will be discussed case-by-case by reviewing protocol deviations during Blind Data Review (BDR) meeting.

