## **Treatment period**

The period from the date of first IP intake to the date of last IP intake is defined as the treatment period.

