#### Follow-up period

The follow-up period is a period lasting from the end of the treatment period until study termination date.

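### No planned AE table separates onset on IP from onset in the 14 days after it, when post-study treatment, possibly opicapone, may already have begun

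*SAP*

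**What the plan says.** **AE window and tables.** SAP Section 5.6.1 uses one undivided window: treatment-emergent AEs are "defined as AEs with the first onset or worsening after the first IP intake until 14 days after the last IP intake". Tables 15.3.1.1 to 15.3.1.10 present them by treatment and overall. The breakdowns are by seriousness, relationship, severity, discontinuation, death, SOC and PT. Onset date and time appear only in the listings.

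**Study periods.** SAP Section 4.6 already draws the relevant line. "The period from the date of first IP intake to the date of last IP intake is defined as the treatment period", and "The follow-up period is a period lasting from the end of the treatment period until study termination date". No AE table uses it.

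**Stopping IP and onward treatment.** SAP Section 2.5 states: "The last IP intake will take place in the evening prior to Visit 6". In the protocol synopsis (Methods / study design), the investigator arranges subsequent treatment at V6 or the EDV, that is, will "either prescribe further opicapone or switch to another treatment". For early discontinuers, footnote 3 to the SAP visit schedule says: "An EDV should be performed as soon as possible (not exceeding 7 days) after early discontinuation".

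**Who is counted where.** Exclusion criterion 7 is "Previous or current use of opicapone". For the Safety Set, SAP Section 3.1 says: "Subjects will be analysed according to actual treatment taken". That set is defined by intake of IP.

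**Medications.** SAP Section 5.3 defines a post-treatment category. Its planned tables cover prior, concomitant and L-DOPA/DDCI medication and tramadol use before the endpoint. Medications started after IP appear only in Listing 16.2.1.11.

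**The concern.** The tail of the TEAE window and the start of post-study treatment can occupy the same days. An event that begins in the tail after a patient has started a new drug would be tabulated under the IP that the patient took earlier. The clearest case is a placebo patient who is prescribed opicapone at V6. Prior use is excluded, so this would be a first exposure, and an event on it would appear in the placebo column.

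Safety and tolerability is a stated secondary objective, and the between-arm AE comparison is read from these tables. As planned, a reader of the tables cannot tell whether the overlap was nil or substantial. They show neither when events began relative to last IP nor how many patients per arm started something new in the tail.

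**Working it through.** The plan states no figure on this point, so there is none to reproduce. The check is a reading of the AE outputs and a count of days.

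**1. AE outputs.**
- Table 15.3.1.1 (overview): treatment and overall, no split by onset period. Its row for TEAEs ongoing at end of study concerns outcome, not onset.
- Tables 15.3.1.2 to 15.3.1.8: SOC and PT by treatment and overall, no split by onset period.
- Tables 15.3.1.9 and 15.3.1.10: the same layout within severity or relationship.
- The table index in SAP Section 10.1 shows no further AE table.

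**2. Completers, nominal timing.** Inputs: V6 on Day 169 and follow-up on Day 183 (visit schedule), last IP the evening before V6, tail of 14 days.
- Last IP = 169 - 1 = Day 168.
- End of window = 168 + 14 = Day 182, so the tail is Days 169 to 182.
- The whole tail falls on or after the visit at which onward treatment is arranged.

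Overlap, with the day of starting counted:
- Start on Day 169: 14 days, 14/182 = 7.7%.
- Start on Day 175: 182 - 175 + 1 = 8 days, 8/182 = 4.4%.
- Start on Day 183 or later: 0 days.

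Over the permitted V6 window (Day 165 to Day 173) the maximum share runs from 14/178 = 7.9% to 14/186 = 7.5%. If onward treatment were first taken in the evening, the maximum would be nearer 13 days.

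**3. Early discontinuers.** Assume that the day of discontinuation is the last IP day D and that onward treatment starts at the EDV, k days later (k = 1 to 7). Overlap = 14 - k + 1 = 15 - k, which is 14 days at k = 1 and 8 days at k = 7. A later start lowers it, down to 0. Two illustrative values of D:
- D = 84: window 98 days, 14/98 = 14.3% or 8/98 = 8.2%.
- D = 28: window 42 days, 14/42 = 33.3% or 8/42 = 19.0%.

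**4. Effect on incidence.** This would need the start date of onward treatment, the share of each arm receiving opicapone or another new drug, and AE rates on and off it. The documents give none of these, so no percentage-point figure can be derived.

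**5. Discontinuation rows.** SAP Section 5.6.1 identifies TEAEs leading to discontinuation by withdrawal of IP or withdrawal from the study. The first cannot apply to an AE that begins after last IP. Only the second remains, so Table 15.3.1.7 and the matching rows of Table 15.3.1.1 are largely unaffected.

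**The case against.** The strongest reply is that the plan contains no error. The tail matches the 2-week follow-up, at which AEs are still recorded, and it captures delayed effects of IP. Onward treatment is only arranged at V6 or the EDV, and no start date is given. Only the synopsis of the protocol is available, and the table shells are separate attachments, so a rule or a split may exist elsewhere. The AE and medication listings allow events to be traced patient by patient among 127 randomised patients, and the relationship tables offer some filter. A cut at last IP also separates by IP status, not by new drug: events after IP would mix delayed, withdrawal, background and new-drug effects.

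Much of this stands. The 14-day definition is sound, and a reader who inferred that the tail should be shortened, or AEs censored when a new drug starts, would be going beyond the documents. A reader might also infer that placebo TEAEs will be inflated and the arm difference narrowed. The documents do not support that: the overlap may be zero, and new drugs may add events to either column.

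Two parts do not stand. Listings do not give a between-arm comparison, and relatedness is judged without knowledge of the allocation, so it filters only partly. And the suggested table keeps events up to last IP, which excludes those on post-study drugs except where onset cannot be dated.

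**Conclusion.** The point holds as a gap in presentation. The SAP's AE tables, as described in its text and index, cannot distinguish events on IP from events in the 14 days after it, and the protocol allows a new treatment, including a placebo patient's first opicapone, to begin in those days. The range of 0 to 14 days in completers rests on nominal visit timing and on last IP the evening before V6. Whether any overlap occurred, and the size and net direction of any effect, are unknown. Severity is low: AE outputs are counts and percentages, no confirmatory result is touched, and TEAEs leading to discontinuation are largely outside the issue.

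**What to change.** Leave the TEAE definition and all main tables as they are, without censoring, and add:

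1. Versions of Tables 15.3.1.1 and 15.3.1.2 restricted to AEs whose onset or worsening is on or before last IP intake. Use the treatment period of SAP Section 4.6 and the same last-IP date as elsewhere in the SAP. Count AEs that cannot be placed as on IP. Serious and related TEAEs are already rows of Table 15.3.1.1, so they need no tables of their own.
2. A footnote to both, giving the number of patients per arm who started post-study opicapone or another new anti-PD drug before the tail ended.
3. A flag in the AE listing for events beginning on or after the start of that drug. Set it to undetermined where the drug's start date is missing or partial, because SAP Section 5.3 by default treats such a medication as concomitant.

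The cost is two tables, one footnote and one flag. AE onset and medication start dates are already collected, and the schedule records both AEs and medications at follow-up. The downside is that delayed or withdrawal effects of IP are absent from the added tables, though they remain in the main ones. Where the last IP date is imputed, the placement of events near the boundary depends on that imputation.

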#### Table 15.3.1.1 Overall Summary of TEAEs – Safety Set

An overview of TEAEs:

- TEAEs
- Ongoing TEAEs at EOS
- Non-serious TEAEs
- Serious TEAEs
- Related TEAEs
- Related Serious TEAEs
- Severe TEAEs
- TEAEs leading to discontinuation
- Related TEAEs leading to discontinuation
- Serious TEAEs leading to discontinuation
- TEAEs leading to death

will be displayed by treatment and overall for the patients in the safety set.

## Table 15.3.1.2 Incidence of TEAEs – Safety Set

Table 15.3.1.3 Incidence of Non-Serious TEAEs - Safety Set

Table 15.3.1.4 Incidence of Serious TEAEs – Safety Set

Table 15.3.1.5 Incidence of Related TEAEs - Safety Set

Table 15.3.1.6 Incidence of Related Serious TEAEs – Safety Set

Table 15.3.1.7 Incidence of TEAEs Leading to Discontinuation – Safety Set

## Table 15.3.1.8 Incidence of TEAEs Leading to Death – Safety Set

TEAEs will be summarised by treatment and overall by displaying the numbers of AEs, as well as counts and percentages of patients having experienced AEs. Percentages will be based on the number of patients in the safety set. SOCs and PTs within each SOC will be ordered by descending number of AEs in the total column.

## Table 15.3.1.9 Incidence of TEAEs by Severity – Safety Set

Table 15.3.1.10 Incidence of TEAEs by Relationship – Safety Set

TEAEs will be summarised as above within each severity/relationship category.

## Listing 16.2.4.1.1 Adverse Events: MedDRA Coding

MedDRA SOC and PTs assigned to each reported AE name will be displayed.

Listing 16.2.4.1.2 Adverse Events: General – Enrolled Set

Listing 16.2.4.1.3 Non-Serious Adverse Events – Safety Set

Listing 16.2.4.1.4 Serious Adverse Events – Safety Set

Listing 16.2.4.1.5 AEs Leading to Discontinuation – Safety Set

Listing 16.2.4.1.6 AEs Leading to Death – Safety Set

All AEs will be displayed by patient including the PT of an AE, onset datetime and stop date, duration and other characteristics of AEs.

